2.9.1 Data handling principles

Zero concentrations will not be included in the geometric mean calculation. Since Tmax is generally evaluated by a nonparametric method, median values and ranges will be given for this parameter.

[figure not shown]
Missing concentration values will be reported as is in data listings. Concentration values below Lower limit of quantitation will be handled as zero in summary statistics, and reported as is in data listings. Any missing pharmacokinetic parameter data will not be imputed.

[figure not shown]
2.9.2 Immunogenicity

[figure not shown]
The presence and/or concentration of anti-MCS110 and/or anti-PDR001 antibodies, at each scheduled time point, will be listed by treatment group, disease and patient. Overall immunogenicity will be summarized when sample size is sufficient. Anti-MCS110 and/or anti-PDR001 antibody data will also be summarized. Number (%) of patients with positive immunogenicity will be calculated.

[figure not shown]
2.10 Patient-reported outcomes

Not applicable.

2.13 Interim analysis

Not applicable.

3 Sample size calculation

Phase Ib

Cohorts of 3 to 6 evaluable patients will be enrolled in the dose-escalation phase including at least six patients at the MTD/RP2D level, as described in [\[CLSZ102X2101-CSP-Section 6.2.3\]](#). Multiple cohorts may be sequentially enrolled to the same dose level. Additional cohorts of 3 to 6 patients may be enrolled at any dose level below the estimated MTD/RP2D for further elaboration of safety and pharmacokinetic parameters as required. At least 15 patients are expected to be treated in the dose escalation phase for the model to have reasonable operating characteristics relating to its estimation of MTD.

Phase II

Approximately 20 patients will initially be enrolled to each of groups 1, 3 and 4. Enrollment may be expanded up to approximately 40 patients in these groups if objective responses (CR or PR) per RECIST v1.1 or irRC are observed (≥ 3 of 20 patients in each of the PD-1/PD-L1 therapy naïve groups or ≥ 2 of 20 patients in the PD-1/PD-L1 therapy resistant group)

([CMCS110Z2102-CSP-Section 2.2]). In Group 2, 20 patients will be enrolled at RP2D, and enrolment may be expanded up to approximately 40 patients if at least 3 pts with CR, PR or SD > 4 months per RECIST v1.1 or irRC are observed. In addition, an exploratory group of 20 patients at a lower dose (1 mg/kg MCS110 in combination with PDR001 300 mg) may be opened if the above mentioned gating criterion is met (Group 2b). The operating characteristics of the designs are provided in [Table 3-1](#) (for Group 1, 3), [Table 3-2](#) (for Group 4), and [Table 3-3](#) (for Group 2 at RP2D), [Table 3-4](#) (for Group 2b).

Table 3-1 Operating characteristics of the design (Group 1, 3)

True ORR	Probability to observe ≥ 3 responses in first 20 patients	Group 1: TNBC Group 3: Endometrial cancer
		probability to observe an ORR $\geq 30\%$ with 40 patients (Overall success rate)
15%	59.5%	1.2%
20%	79.4%	8.7%
25%	90.9%	28.4%
30%	96.5%	55.8%
40%	99.6%	92.8%
50%	100.0%	99.7%

Table 3-2 Operating characteristics of the design (Group 4)

True ORR	Probability to observe ≥ 2 responses in first 20 patients	Groups 4: resistant melanoma
		probability to observe an ORR $\geq 15\%$ with 40 patients (Overall success rate)
7.5%	44.9%	7.1%
15%	82.4%	54.2%
20%	93.1%	81.5%
30%	99.2%	98.6%
40%	99.9%	99.9%
50%	100.0%	100%

Table 3-3 Operating characteristics of the design (Group 2 at RP2D)

True CBR	Probability to observe ≥ 3 responses (CR, PR or SD > 4 months) in first 20 patients	Group 2: Pancreatic cancer
		probability to observe a CBR $\geq 15\%$ with 40 patients
7.5%	18.6%	5.5%
15%	59.5%	46.1%
20%	79.4%	73.4%
30%	96.5%	96.1%

Table 3-4 Operating characteristics of the design (Group 2b)

True CBR	Groups 2b: Pancreatic cancer
	probability to observe a CBR $\geq 15\%$ with 20 patients
7.5%	18.6%
15%	59.5%
20%	79.4%
30%	96.5%

4 Change to protocol specified analyses

The following section have been updated in comparison to first SAP

Section 1.1 Study design

Section 1.2 Study objectives and endpoints

Section 2.1 Data analysis general information

Section 2.1.1 General definitions

Section 2.2 Analysis sets/Withdrawal of ICF/Subgroups

Section 2.4.1 Study treatment/compliance

Section 2.5.1 Primary endpoints

Section 2.5.2 Phase II part (Secondary endpoint)

Section 2.5.4 Supportive analyses

Section 2.7.1 Secondary endpoints

Section 2.8 Safety analyses

Section 2.8.3 Laboratory data XXXXXXXXXX

Section 3 Sample size calculation

Section 5.5 Rule of exclusion criteria of analysis sets

Section 1.1 Study design

- Updated the study design for Phase II part per protocol amendment version 5

Section 1.2 Study objectives and endpoints

- Secondary objectives, Phase II part: changed endpoint for Group 2 (Pancreatic cancer) to CBR instead of ORR

Section 2.1 Data analysis general information

- Add R version which will be used for Bayesian analyses for Phase II part.

Section 2.1.1 General definitions

- Definition of on-treatment and post-treatment assessment/event

Section 2.2 Analysis sets/Withdrawal of ICF/Subgroups

- Per-protocol Set was planned as per the protocol, but outputs were not generated because no analyses were conducted based on per-protocol set
- Add section 2.2.5 Withdrawal of Informed Consent

Section 2.4.1 Study treatment/compliance

- Definition of last date of exposure of study drug/treatment (+ 20 days instead of + 21)

Section 2.5.1 Phase II part (Primary endpoint)

- Change of group 2 (Pancreatic cancer) endpoint to CBR instead of ORR

Section 2.5.2 Phase II part (Secondary endpoint)

- Change of group 2 prior distribution
- Update design of group 2 per protocol amendment version 5

Section 2.5.4 Supportive analyses

- Change to be not applicable cause supportive analyses were not conducted.

Section 2.7.1.2 Phase II (Secondary efficacy objectives)

[figure not shown]
- Group 2 (pancreatic cancer) secondary endpoint changed to CBR

[figure not shown]
Section 2.8 Safety analyses

- Definition of on-treatment period changed from including 90 days to 30 days after last dose in line with all other IO studies and reporting standards.
- Definition of post-treatment period changed from starting at day 91 after last dose of study medication to 31 days after last administration of study treatment in line with all other IO studies and reporting standards.

Section 2.8.3 Laboratory data

- Both fasting glucose and non-fasting glucose will be summarized and listed for information integrity. Both of glucoses will be combined and reported based on CTCAE v4.03. Fasting glucose values will be flagged in the listing.

Section 3 Sample size calculation

- Update study design for phase II part per protocol amendment version 5

Section 5.5 Rule of exclusion criteria of analysis sets

- Table for protocol deviations leading to exclusion from analysis set was removed due to no such PDs were collected

5 Appendix

5.1 Imputation rules

5.1.1 Study drug

5.1.2 AE date imputation

A missing AE start date will be imputed using the following logic matrix described in [Table 5-1](#).

Table 5-1 Imputation rules for a partially missing AE start date

	AEM MISSING	AEM < TRTM	AEM = TRTM	AEM > TRTM
AEY MISSING	No imputation	No imputation	No imputation	No imputation
AEY < TRTY	(D)	(C)	(C)	(C)
AEY = TRTY	(B)	(C)	(B)	(A)
AEY > TRTY	(E)	(A)	(A)	(A)

AEM: Month AE started; AEY: Year AE started
TRTM: Month treatment started; TRTY: Year treatment started

[Table 5-2](#) is the legend to the logic matrix shown in [Table 5-1](#) and details the relationship of AE start date to study treatment start date.

Table 5-2 Imputation legend and AE/treatment start date relationship

	AE start date relationship	Imputation
(A)	After treatment start or Uncertain	MAX(01MONYYYY, TRTSTD + 1)
(B)	Uncertain	TRTSTD + 1
(C)	Before treatment start	15MONYYYY
(D)	Before treatment start	01JULYYYY
(E)	After treatment start	01JANYYYY

Before treatment start: Partial date indicates AE start date is prior to treatment start date.

After treatment start: Partial date indicates AE start date is after treatment start date.

Uncertain: Partial date insufficient to determine relationship of AE start date to treatment start date.

No imputation will be performed for AE end dates.

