7.1 Study flow and visit schedule

[Table 7-1](#) lists all of the assessments and indicates with an “X”, the visits when they are performed. All data obtained from these assessments must be supported in the patient’s source documentation. The table (“Category” column) indicates which assessments produce data to be entered into the clinical database (D) or remain in source documents only (S).

No CRF will be used as a source document.

Screening/baseline evaluations must be performed ≤ 21 days before Cycle 1 Day 1, except for baseline radiological evaluations which must be done within 28 days. Assessments performed as part of the screening evaluations and within 3 days prior to the first dose of study treatment, are not required to be repeated on the first dosing day.

Laboratory and radiological assessments performed as part of standard of care prior to signing informed consent may be used if performed within 21 days and 28 days respectively, of Cycle 1 Day 1.

During the course of the study visits, test and/or procedures should occur on schedule whenever possible. A visit window of ± 7 days is allowed. If the infusion of MCS110 and/or PDR001 is delayed, the visits assessments will be shifted accordingly. On PK collection days the windows are provided in [Section 7.2.3](#).

Radiological assessments must be performed ± 1 week of the scheduled date of the assessment.

For Japan only, patients are required to be hospitalized during Cycle 1.

Visit name	Category	Protocol Section	Screening Phase	Treatment Phase														Follow-up	Disease Progression F/U	Survival F/U	
			Screening	Cycle 1					Cycle 2		Cycle 3	Cycle 4					Subsequent cycles	EOT			Safety F/U
Day of cycle			-21 to -1	1	2	4	8	15	1	15	1	1	2	4	8	15	1				
Prior/concomitant medications, surgery and medical procedures	D	7.1.1.2 7.1.5 and 6.4	X	Continuous ¹																	
Physical examination	S	7.2.2.1	X	X			X	X	X	X	X	X					X	X			
Height	D	7.2.2.3	X																		
Weight	D	7.2.2.3	X	X					X		X	X					X	X			
Vital signs	D	7.2.2.2	X	X			X	X	X	X	X	X					X	X			
Performance status	D	7.2.2.4	X	X					X		X	X					X	X			
Hematology	D	7.2.2.5.1	X	X			X	X	X	X	X	X			X		X	X			
Chemistry	D	7.2.2.5.2	X	X			X	X	X	X	X	X			X		X	X			
Coagulation	D	7.2.2.5.6	X	Only if clinically significant														X			
Urinalysis	D	7.2.2.5.3	X	X					X		X	X					X	X			
Thyroid function	D	7.2.2.5.4	X	X					X		X	X					X	X			

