8.1 Adverse events

8.1.1 Definitions and reporting

An adverse event is defined as the appearance of (or worsening of any pre-existing) undesirable sign(s), symptom(s), or medical condition(s) that occur after patient's signed informed consent has been obtained.

Abnormal laboratory values or test results occurring after informed consent constitute adverse events only if they induce clinical signs or symptoms, are considered clinically significant, require therapy (e.g., hematologic abnormality that requires transfusion or hematological stem cell support), or require changes in study medication(s).

Adverse events that begin or worsen after informed consent should be recorded in the Adverse Events CRF. Conditions that were already present at the time of informed consent should be recorded in the Medical History page of the patient's CRF. Adverse event monitoring should be continued for 150 days after the last dose of PDR001 or 90 days after the last dose of MCS110 for patients who stopped PDR001 and continued MCS110 alone for more than 60 days).

After initiation of new post-treatment antineoplastic therapy, only AEs suspected to be related to study treatment will be collected in the Adverse Events CRF.

Adverse events (including lab abnormalities that constitute AEs) should be described using a diagnosis whenever possible, rather than individual underlying signs and symptoms. When a clear diagnosis cannot be identified, each sign or symptom should be reported as a separate Adverse Event.

Adverse events will be assessed according to the Common Terminology Criteria for Adverse Events (CTCAE) version 4.03. If CTCAE grading does not exist for an adverse event, the severity of mild, moderate, severe, and life-threatening, corresponding to Grades 1 - 4, will be used. CTCAE Grade 5 (death) will not be used in this study but is collected as a seriousness criteria; rather, information about deaths will be collected through a Death form.

The occurrence of adverse events should be sought by non-directive questioning of the patient (subject) during the screening process after signing informed consent and at each visit during the study. Adverse events also may be detected when they are volunteered by the patient (subject) during the screening process or between visits, or through physical examination, laboratory test, or other assessments. As far as possible, each adverse event should be evaluated to determine:

- The severity grade (CTCAE Grade 1-4)

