- Its duration (Start and end dates)
- Its relationship to the study treatment (Reasonable possibility that AE is related: No, Yes)
- Action taken with respect to study or investigational treatment (none, dose adjusted, temporarily interrupted, permanently discontinued, unknown, not applicable)
- Whether medication or therapy was given (no concomitant medication/non-drug therapy, concomitant medication/non-drug therapy)
- Outcome (not recovered/not resolved, recovered/resolved, recovering/resolving, recovered/resolved with sequelae, fatal, unknown)
- Whether it is serious, where a serious adverse event (SAE) is defined as in [Section 8.2.1](#) and which seriousness criteria have been met.

All adverse events should be treated appropriately. If a concomitant medication or non-drug therapy is given, this action should be recorded on the Adverse Event CRF.

Once an adverse event is detected, it should be followed until its resolution or until it is judged to be permanent, and assessment should be made at each visit (or more frequently, if necessary) of any changes in severity, the suspected relationship to the study treatment, the interventions required to treat it, and the outcome.

Progression of malignancy (including fatal outcomes), if documented by use of appropriate method (for example, as per irRC or as per RECIST), should not be reported as a serious adverse event.

Adverse events separate from the progression of malignancy (example, deep vein thrombosis at the time of progression or hemoptysis concurrent with finding of disease progression) will be reported as per usual guidelines used for such events with proper attribution regarding relatedness to the drug.

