2.8.1 Adverse events (AEs)

Adverse events will be coded and graded using the latest version of MedDRA and CTCAE, respectively, available at the time of reporting. If CTCAE grading does not exist for an AE, grades 1, 2, 3, or 4 corresponding to the severity of mild, moderate, severe, and life-threatening, respectively, will be used. CTCAE grade 5 (death) will not be used in this study. Death information will be collected on the "Death" eCRF page.

Abnormal laboratory values or test results occurring after informed consent constitute adverse events only if they induce clinical signs or symptoms, are considered clinically significant, require therapy (e.g., hematologic abnormality that requires transfusion or hematological stem cell support), or require changes in study medication(s).

All AEs will be listed. All AE summaries will be summarized (frequency counts and percentages) by system organ class and/or preferred term, and maximum severity grades, unless noted otherwise.

Summary tables for AEs have to include only AEs that started or worsened during the on-treatment period, the treatment-emergent AEs. However, all safety data (including those from the pre and post-treatment periods) will be listed and those collected during the pre-treatment and post-treatment period are to be flagged.

The following AE summaries will be produced:

- AEs regardless of study drug relationship (including CTC grade 3-4)
- AEs suspected to be study drug related (including CTC grade 3-4)
- AEs regardless of study drug relationship leading to discontinuation of study drug
- AEs which are not SAEs regardless of study drug relationship (for CTRD)
- SAEs regardless of study drug relationship

A patient with multiple CTC grades for an AE will be summarized under the maximum CTC grade recorded for the event. A subject with multiple occurrences of an AE is counted only once in the AE category (e.g. system organ class, preferred term).

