5.1.4 Prior therapies date imputation

Consider specific imputation rules for partial dates.

Start date:

The same rule which is applied to the imputation of AE/concomitant medication ([Section 5.1.2](#)) start date will be used with the exception that scenario (B) will be replaced to be 'start date of study treatment - 1'.

End Date:

Imputed date = min (start date of study treatment, last day of the month), if day is missing;

Imputed date = min (start date of study treatment, 31DEC), if month and day are missing.

If the end date is not missing and the imputed start date is after the end date, use the end date as the imputed start date.

If both the start date and the end date are imputed and if the imputed start date is after the imputed end date, use the imputed end date as the imputation for the start date.

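### SAP 5.1.2 can date an adverse event that ended before the first dose to the day after it, because the start-date imputation never checks a recorded end date

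*SAP*

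**What the plan says.** SAP 5.1.2 compares the month and year of a partial AE start date with those of treatment start (Table 5-1) and assigns a date from the resulting cell (Table 5-2). Cell (B) applies when the years agree and the AE month either equals the treatment month or is missing. It is labelled uncertain, which the table note explains as "Partial date insufficient to determine relationship of AE start date to treatment start date", and the imputed start is one day after treatment start. The section's only statement about end dates is "No imputation will be performed for AE end dates".

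SAP 2.8 starts the on-treatment period on the day of first dose, and SAP 2.8.1 says "Summary tables for AEs have to include only AEs that started or worsened during the on-treatment period". Neither section sets a condition on the end date.

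SAP 5.1.4 borrows the same matrix for prior therapies, changes cell (B) to the day before treatment, and adds a check: "If the end date is not missing and the imputed start date is after the end date, use the end date" as the imputed start. SAP 2.4.2 and 5.1.3 apply the AE rule to concomitant medications without that check.

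On data collection, Protocol 8.1.1 says "Adverse events that begin or worsen after informed consent should be recorded in the Adverse Events CRF", and asks for start and end dates of each event. Protocol 7.1 says "Screening/baseline evaluations must be performed ≤ 21 days before Cycle 1 Day 1"; baseline imaging may be up to 28 days before.

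**The concern.** The uncertainty label is right only while nothing else is known about the event. If the record carries a complete end date before first dose, the event must have started before treatment, and its timing is settled. The rule still moves the start to after dosing. This creates an impossible record, with start later than end, and turns a pre-treatment event into a treatment-emergent one.

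At stake are the descriptive AE tables. AE incidence is among the Phase Ib primary variables (Protocol 10.4.1, SAP 2.5.1.1) and the groups are small, so one patient moves a rate visibly. The concomitant medication summary in SAP 2.4.2 counts therapies starting on or after the start of treatment. A medication stopped before dosing whose partial start date falls in cell (B) can be counted there for the same reason.

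**Working it through.** The documents give no figure to reproduce here, so the check applies Tables 5-1 and 5-2 literally.

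**1. Worked example.** First dose 15 March 2017; AE end date 10 March 2017, complete; AE start recorded as March 2017 with the day missing.
- The year and month match, so cell (B) applies.
- Imputed start = first dose + 1 day = 16 March 2017.
- Imputed start minus recorded end = 16 − 10 = 6 days, so the event starts six days after it ended.
- 16 March is on or after first dose, so the event counts as treatment-emergent under SAP 2.8 and 2.8.1.
- If only the year 2017 is known, cell (B) applies again and the result is the same.

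**2. Which cells can fail.** Cells (C) and (D) give dates before treatment. Cells (A) and (E) apply only when the recorded start month or year is already after treatment start. Only cell (B) can move an event that ended before dosing.

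**3. How often cell (B) catches such a record, given that one exists.** Take every start and end pair lying wholly in the 21 days before first dose, for each first-dose date from 1 July 2016 to 10 January 2019.
- Pairs per first-dose date: 21 × 22 / 2 = 231.
- First-dose dates: 924.
- Total: 924 × 231 = 213,444.

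| Missing part of start date | Imputed to first dose + 1 | With the 5.1.4 check |
|---|---|---|
| Day | 111,969 / 213,444 = 52.5% | 0 |
| Day and month | 204,677 / 213,444 = 95.9% | 0 |

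These shares assume that all pairs are equally likely. They are conditional on a partial start date together with a complete pre-dose end date, and say nothing about how many such records the trial holds.

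**4. What the check changes.** In the example, 16 March is after 10 March, so the start becomes 10 March and the event is pre-treatment. If the end date were 15 March, the dosing day, the start would become 15 March and the event would remain treatment-emergent. With a missing end date, or one after the dosing day, the imputed start is unchanged.

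**5. Size per patient.** One patient in a Phase II group of 20 is 1/20 = 5 points. Phase Ib dose levels had 6, 12, 12, 13, 6 and 11 patients (Protocol, study status under Amendment 04). One patient is therefore 1/6 = 16.7 points in the two smallest, and between 1/13 = 7.7 and 1/11 = 9.1 points in the other four.

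**The case against.** The trigger is narrow. The event must begin or worsen after consent, lack part of its start date although it arose under study observation, have a complete end date before dosing, and fall in the treatment month or year. Protocol 9.3 and 9.4 plan automatic discrepancy checks and queries for missing values, so many partial dates should be resolved before any imputation. SAP section 1 places derived-variable specifications in the Programming Datasets Specifications (PDS), which was not supplied and may already contain a start-not-after-end check. Dating uncertain onsets to after dosing also errs towards over-reporting, a defensible choice for safety.

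Most of this stands as an argument about size. It does not repair the rule as written. Queries reduce the cases without excluding them. The SAP spells out the check for prior therapies and omits it for AEs, so a programmer following it literally would leave it out. The conservative default is reasonable when the end date is missing or falls on or after first dose, and the check leaves those events treatment-emergent.

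A reader might infer more than the documents support:
- **That the event enters every treatment-emergent table.** It enters only tables whose other criteria it meets. An event resolved before dosing should not be judged drug-related or lead to discontinuation of study drug, and it cannot be in both the SAE and the non-SAE table.
- **That each case adds a fixed 5 or 17 points.** SAP 2.8.1 counts a patient once per AE category, so a patient who has the same event on treatment adds nothing. The figures are maxima.
- **That all medications stopped before dosing count as concomitant.** Only those with a partial start date in cell (B) are affected.
- **That the Phase Ib dose decision is in doubt.** DLTs are discussed and agreed case by case (Protocol 6.2.3.1) and summarised on the dose-determining set (SAP 2.5.2.1.1).

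**Conclusion.** The point holds as a minor one. As written, SAP 5.1.2 gives a wrong result for an AE with a cell (B) start date and a complete end date before first dose, and nothing in the supplied documents overrides it. The misclassified event counts in the all-causality table and in either the SAE or the non-SAE table. The effect is at most 5 points per affected patient in a 20-patient group and at most 17 points in the two 6-patient dose levels. The number of affected records is not given and is probably small.

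No DLT, dose decision or efficacy result is shown to change; what can change is descriptive AE counts and the concomitant medication summary. The conclusion rests on a literal reading of the SAP and on the PDS adding no check of its own.

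**What to change.** Add to SAP 5.1.2, and so by reference to 5.1.3, the rule already in 5.1.4: "If the end date is not missing and the imputed start date is after the end date, use the end date" as the imputed start. Only events and medications shown by their own end date to precede first dose change status. Those with a missing end date, or one on or after first dose, stay where the present rule puts them.

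Align the PDS with this sentence, or confirm that it already carries the check.

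The cost is one sentence in the SAP and one line of code. SAP section 1 already provides the route: an amendment before database lock, or an addendum after it.
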